### **Data Collection and Follow-up for Withdrawn Subjects**

Even though subjects may be withdrawn prematurely from the study, an attempt will be made to collect at least survival data on such subjects throughout the protocol defined follow-up period. Such data is important to the integrity of the final study analysis, since early withdrawal could possibly be related to the safety profile of the study. If a subject withdraws consent to participate in the study, attempts will be made to obtain permission to record at least survival data up to the protocol-described end of subject follow-up period.

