### **Post randomization**

The recipients assigned to continue with tacrolimus and MMF will be routinely followed at our outpatient Transplant center with monthly labs. In addition to the baseline pre-randomization labs, at 6, 12 and 24 months post randomization, peripheral blood leukocytes will be obtained to study lymphocytes functional activity and to characterize lymphocytes subpopulations by flow cytometry analysis.

Post randomization, the recipients assigned to switch from tacrolimus to sirolimus and continue with MMF will be routinely followed at our Transplant center with monthly labs. Furthermore, during the period of conversion from tacrolimus to sirolimus, weekly labs will be obtained to monitor renal function and bone marrow function. In addition to the baseline pre-randomization labs, and labs collected at 6, 12, 24, 36, and 48 months post randomization, peripheral blood leukocytes will be obtained to study lymphocytes functional activity to characterize lymphocytes subpopulations by flow cytometry analysis and urine will be collected to assess tubular toxicity by evaluating urinary biomarkers.

Both groups of patients will be followed for 4 years post-randomization. In addition to monitoring renal allograft function, we will evaluate the incidence of acute rejection, patient and graft survival, the impact of CI conversion on the lipid profile, the incidence of hypertension, malignancies, opportunistic infections and post-transplant DM.

Furthermore, with the peripheral leukocytes obtained at baseline prior to randomization and at 6, 12, 24, 36, and 48 months post-randomization we will investigate possible modifications of lymphocytes function and of the lymphocytes subpopulations that might have occurred as a consequence of the switch from tacrolimus to sirolimus.

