## **Early Withdrawal of Subjects**

### **When and How to Withdraw Subjects**

Subjects may withdraw from the clinical trial at any time for any reason with no prejudice to their medical care. Subjects may also be stopped in the study without their consent if their medical care requires they be. Also, the Institutional Review Board (IRB) may stop the study at any time and all subjects will be returned to taking tacrolimus and followed for safety. Subjects will be informed of why they are being stopped.

Subjects non-compliant with medications and clinic follow-ups will be withdrawn from the study.

Subjects with post-transplant complications such as malignancy or infections that require modification or withdrawal of maintenance immunosuppression will be withdrawn from the study.

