### **Stopping Rules**

Subjects diagnosed with two acute renal allograft rejection episodes post conversion from tacrolimus to sirolimus will be stopped from participating in the study and will be switched back to tacrolimus.

Subjects that develop significant side effects secondary to sirolimus (severe thrombocytopenia (platelets count <50, 000); severe hyperlipidemia not controlled by the use of statins or other cholesterol lowering agents; worsening proteinuria or severe de-novo proteinuria) will have sirolimus stopped and patients will be switched back to tacrolimus.

Subjects developing post-transplant infections (i.e., UTI, CMV, HSV, EBV, HCV, HBV, HIV, PCP), that in the opinion of the investigator are detrimental to the subject and their participation in this research trial, will be stopped from participating in this study.

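### Withdrawn subjects need not be followed for acute rejection, and the plan does not say how they enter the primary comparison, so the result may be biased by an amount and in a direction the documents cannot fix

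*Combined protocol and SAP*

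**What the plan says.** The Research Objective section makes the incidence of acute cellular rejection the primary aim. It does not say whether patients with a rejection or rejection episodes are counted. The Post randomization section states: "Both groups of patients will be followed for 4 years post-randomization".

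Several rules end participation. Under When and How to Withdraw Subjects: "Subjects non-compliant with medications and clinic follow-ups will be withdrawn from the study", and "Subjects with post-transplant complications such as malignancy or infections that require modification or withdrawal of maintenance immunosuppression will be withdrawn from the study". Under Stopping Rules, subjects with infections "that in the opinion of the investigator are detrimental to the subject and their participation in this research trial, will be stopped from participating". These rules are worded alike for both arms. One rule applies to converted subjects only: "Subjects diagnosed with two acute renal allograft rejection episodes post conversion from tacrolimus to sirolimus will be stopped from participating in the study". Subjects with listed sirolimus side effects "will have sirolimus stopped and patients will be switched back to tacrolimus", but the text does not say whether they leave the study.

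After withdrawal, "an attempt will be made to collect at least survival data on such subjects throughout the protocol defined follow-up period". The stated reason is that such data matter to the final analysis, "since early withdrawal could possibly be related to the safety profile of the study".

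The Adverse Event Reporting Period section closes reporting 30 days after the last study treatment. The sections on recording events and on post-study events reach later events only where a link to the study is thought possible or reasonable.

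The Statistical Analysis section gives t tests, chi-square tests and a multivariable logistic regression. It defines no analysis set, censoring rule or rule for unknown rejection status.

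**The concern.** Non-adherence and changed immunosuppression both bear on the chance of rejection, so subjects who leave for these reasons are unlikely to be a random sample of their arm. The protocol recognises that withdrawal may be informative, yet sets the required data at survival and does not extend it to the primary outcome.

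A chi-square test needs a yes or no for each subject. Someone must therefore decide whether a withdrawn subject without a known rejection counts as event-free or is dropped. In an open-label trial with no written rule, that choice may be made after the data are seen, and it moves the primary estimate.

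**Working it through.** **Inputs from the documents.** 275 randomised 2:1; 4 years of follow-up; chi-square comparison. The Randomization section does not name the larger arm, but the Biopsy section counts (46 tacrolimus, 93 sirolimus) imply sirolimus, so I take 92 tacrolimus and 183 sirolimus. The 275 cannot be reproduced, because no alpha, power, rejection rate, effect size or dropout is given.

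**Assumed inputs.** Four-year rejection risk p of 8% on tacrolimus and 18% on sirolimus; constant hazards; four-year withdrawal risk q as listed; rejection hazard after withdrawal multiplied by k.

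**Formulas, per arm.** r = -ln(1-p)/4 and w = -ln(1-q)/4.

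- Rejection seen before withdrawal: O = r/(r+w) × [1 - (1-p)(1-q)]
- Withdrawn without rejection: W = w/(r+w) × [1 - (1-p)(1-q)]
- Rejections after withdrawal: U = integral from 0 to 4 of w·exp(-(r+w)u)·[1 - exp(-k·r·(4-u))] du
- True risk = O + U; coded event-free = O; excluded = O/(1-W)

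**Example, 20% withdrawal in each arm, k = 1.** Here w = 0.0558.

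- Tacrolimus: r = 0.0208, O = 0.272 × 0.264 = 7.2%, W = 19.2%, excluded = 7.2/80.8 = 8.9%.
- Sirolimus: r = 0.0496, O = 0.471 × 0.344 = 16.2%, W = 18.2%, excluded = 16.2/81.8 = 19.8%.
- Differences: 9.0 coded event-free, 10.9 excluded. Unseen rejections: about 0.8 on tacrolimus and 3.3 on sirolimus.

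**Results** (sirolimus minus tacrolimus, percentage points):

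| Withdrawal, tacrolimus / sirolimus | k | True | Event-free | Excluded |
|---|---|---|---|---|
| 5% / 5% | 1 | 10.0 | 9.8 | 10.2 |
| 10% / 10% | 1 | 10.0 | 9.5 | 10.4 |
| 20% / 20% | 1 | 10.0 | 9.0 | 10.9 |
| 15% / 25% | 1 | 10.0 | 8.3 | 11.7 |
| 25% / 15% | 1 | 10.0 | 9.7 | 10.1 |
| 20% / 20% | 2 | 10.8 | 9.0 | 10.9 |
| 25% / 15% | 2 | 10.2 | 9.7 | 10.1 |
| 20% / 20% | 3 | 11.5 | 9.0 | 10.9 |

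With k = 1 the two codings fall on either side of the truth in these rows. In the last two rows both fall below it.

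**Power and false positives** (simulation, uncorrected chi-square, two-sided 0.05 assumed). Power is 62% with full follow-up and 57% under either coding at 20% / 20%. It is 50% (event-free) or 65% (excluded) at 15% / 25%, and 63% or 49% at 25% / 15%. With equal true risk of 10%, the false-positive rate is 4.7% with full follow-up, and 5.2% or 5.0% at 15% / 25%.

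**Partial capture, k = 1.** If half of the post-withdrawal rejections are found, event-free coding gives 9.5 (20% / 20%) and 9.2 (15% / 25%). If found rejections count and other withdrawn subjects are dropped, the figures are 11.3 and 12.6, further from the truth than with no capture.

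**Direction, by a simpler check.** Let risk in retained subjects be 8% in both arms, with 25% withdrawn on sirolimus and 10% on tacrolimus.

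- Later risk 20% in both: true difference (0.75×8 + 0.25×20) - (0.90×8 + 0.10×20) = 11.0 - 9.2 = +1.8. Excluded gives 0.0, and event-free gives 6.0 - 7.2 = -1.2. Both are too low.
- Later risk 2% on sirolimus and 20% on tacrolimus: true 6.5 - 9.2 = -2.7, against 0.0 and -1.2. Both are too high.

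**Time-to-event check.** At 20% / 20% with k = 2, Kaplan-Meier censored at withdrawal gives 10.0 against a true 10.8. The method alone does not remove the bias.

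**The case against.** The survival wording is a floor, so rejection data may be collected too. This is one centre with routine clinic follow-up. Tacrolimus and MMF are listed under Study drugs, so a withdrawn subject still taking either may arguably remain inside the adverse-event window, and a rejection could be recorded there. At equal withdrawal up to 20% with unchanged hazard, the shift is at most about 1 point on an assumed 10, and about four events are unseen even if none is captured.

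Much of this stands. A reader might infer that later rejections will not be recorded; the documents do not say that. What they lack is any requirement to record them. The adverse-event route is uncertain for subjects still on tacrolimus or MMF, and otherwise depends on judged relatedness. The general 4-year statement does not settle it either, because the withdrawal section is the specific rule.

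A reader might also infer that the sirolimus-only stopping rules bias the primary result. The two-rejection stop cannot lose a first rejection, since the event has already happened. Only if episodes are counted, which the Research Objective leaves open, would it truncate the primary outcome in the converted arm alone. The side-effect switch-back is not stated to end participation.

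**Conclusion.** The gap is real: primary-outcome ascertainment is not required after mandatory withdrawals that are plausibly linked to rejection, and the coding of those subjects is left open. Size and direction cannot be fixed from the documents, because every rate above is assumed. In these illustrations, equal withdrawal with unchanged hazard distorts little. At 15% against 25%, the choice of coding alone moves the estimate by 11.7 - 8.3 = 3.4 points.

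Two stronger readings should be resisted. One is that the trial will be seriously biased for or against sirolimus: that needs strongly unequal withdrawal or a marked change in risk after withdrawal, which the documents neither predict nor rule out. The other is that reporting both codings would bound the truth: the rows with raised hazard show that it need not. This is a cheap improvement, held with medium confidence.

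**What to change.** Leave all treatment stopping and switch-back rules unchanged.

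1. Amend the section on follow-up of withdrawn subjects, and the participation wording under When and How to Withdraw Subjects and Stopping Rules, to separate stopping study drug from leaving the study. For every randomised subject who has not withdrawn consent to data collection, obtain acute rejection, graft loss, eGFR and proteinuria to month 48 from the transplant-centre record. Say whether switched-back subjects remain in the study.
2. Make the primary analysis all randomised subjects in their assigned arm. Define the outcome per patient as at least one rejection by month 48, counting every ascertained rejection before or after withdrawal.
3. For subjects still lost, name time to first rejection, censored at last known rejection status, as the primary handling. Add sensitivity analyses under a raised post-withdrawal hazard, event-free coding and exclusion, and state that the last two need not bracket the truth. Censoring supplements continued ascertainment and does not replace it.

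The cost is an IRB amendment, new consent wording, possibly re-consent (the Biopsy section shows subjects already enrolled) and chart abstraction. Data will stay incomplete for those who stop attending clinic. Keeping switched-back subjects in their assigned arm dilutes the on-drug contrast somewhat, which a secondary on-treatment analysis can show.

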## **Study drugs**

### **Sirolimus (Rapamune®)**

Sirolimus will initially be given at a dose of 2-4 mg orally (PO) daily. The dose will be modified to achieve 24 hours trough concentrations of 6-10 ng/ml by HPLC assay. This medication will be given in an open label fashion. The first dose of sirolimus will be given at the time of randomization to those patients assigned to have tacrolimus switched to sirolimus.

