### **Research Objective**

The aim of the present study is to prospectively investigate the impact of CI conversion (tacrolimus→sirolimus) between 6 and 24 months post-transplant on the incidence of acute cellular rejection, renal allograft function and lymphocytes function.

Primary aim of the study is:

to investigate the impact of CI conversion (tacrolimus→sirolimus) on the incidence of acute cellular rejection.

Secondary aims of the study are:

- i) evaluate whether CI conversion (tacrolimus→sirolimus) contributes positively or negatively on the renal allograft function calculated with e-GFR and proteinuria;
- ii) patient and graft survival ;
- iii) evaluate if CI conversion impacts on lipid profile, incidence of hypertension, malignancies, and opportunistic infections and post-transplant DM;
- iv) evaluate possible modifications of lymphocytes function before and after conversion (tacrolimus→sirolimus)
- v) assess tubular toxicity by evaluating urinary biomarkers

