## **Biopsy**

Chronic nephrotoxicity from calcineurin-inhibitors (CI) has been implicated as a principal cause of post-transplant renal dysfunction and it is characterized by an irreversible and progressive tubular atrophy, interstitial fibrosis, and focal hyalinosis of small renal arteries and arterioles. Furthermore, chronic nephrotoxicity from CI has been documented in all non-renal transplants and the chronic renal failure secondary to the use of CI has been associated with an increase in mortality by a factor of more than four.

The present proposal is to identify those subjects already participating in this study who are willing to undergo a kidney biopsy with the aim of evaluating renal allograft pathology and renal allograft tissue gene expression profiles of the two groups of patients maintained on Tacrolimus/ MMF or switched to SRL/MMF. Performing kidney biopsies on the subjects who consent for the procedure will allow us to address the effect of immunosuppressive modifications on renal allograft pathology at 24 months post randomization. We also plan to obtain renal allograft biopsies at 12 months post-transplant (standard of care) in order to establish a baseline parameter for to compare the 24 month sample. An additional biopsy at 48 months will allow us to examine long term results of graft function. We also plan to obtain renal allograft biopsies to be stored in RNA later to further extend our knowledge on the effect of CI free immunosuppression on gene expression profiles.

Obtaining renal allograft tissue samples at 24 and 48 months post randomization can have potential important ramifications to help explain the mechanisms of fibrosis and tubular atrophy typically associated with CI and the role of CI elimination with the substitution of SRL. All data will then be analyzed comparing gene expression profiles of peripheral blood (Paxgene tubes are routinely collected at the different time points as part of the original study). Based on power analysis, we will perform 24 and 48 months post randomization biopsies in 70% of the total subjects enrolled in the study (approximately 46 subjects from the tacrolimus/MMF group and approximately 93 subjects from the sirolimus/MMF group).

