## **Treatment of Acute Renal Allograft Rejection**

Initial treatment for biopsy-confirmed acute rejection for all subjects will be pulse corticosteroids (methylprednisolone 500 mg IV x 3 days), tapered to a dose of 20 mg prednisone by day 7, unless the severity of the initial episode warrants use of anti-T-lymphocyte antibody (OKT3 or Thymoglobulin). Recurrent rejection will be treated with anti-T-lymphocyte antibody (OKT3 or Thymoglobulin).

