## **Internal Data and Safety Monitoring Plan**

An Internal Data and Safety Monitoring Plan, is based on the GCRC and some NIH guidelines for Data Safety Monitoring. All physicians associated with the Solid Organ Transplant Department are listed as either the PI or Sub-I's with this study. The plan approved by the IRB would utilize the statistical analyst along with the current QA committee to review the research SAE's and AE's.

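### The drugs are open label and no masked reading is specified for the scheduled 24- and 48-month biopsies, so a reader who knows the arm can bias the between-arm pathology comparison

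*Combined protocol and SAP*

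**What the plan says.** All three maintenance drugs are open label. The Sirolimus section reads "This medication will be given in an open label fashion", and the Tacrolimus and Mycophenolate Mofetil sections use the same wording.

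The primary aim, under Research Objective, is "to investigate the impact of CI conversion (tacrolimus→sirolimus) on the incidence of acute cellular rejection". No diagnostic criterion or grading scale follows. A link to histology appears only in the rejection-treatment section: "Initial treatment for biopsy-confirmed acute rejection for all subjects will be pulse corticosteroids".

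The Biopsy section adds tissue sampling in consenting subjects with "the aim of evaluating renal allograft pathology and renal allograft tissue gene expression profiles of the two groups of patients". The samples are meant to "help explain the mechanisms of fibrosis and tubular atrophy typically associated with CI". On numbers it says "we will perform 24 and 48 months post randomization biopsies in 70% of the total subjects enrolled in the study", given as about 46 tacrolimus and 93 sirolimus subjects.

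The protocol does not mention coded slides, masked or central reading, an adjudication committee, or any rule that keeps the arm from the reader. The only review body described is the internal QA committee with the statistical analyst, and its remit is adverse events.

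**The concern.** Open-label treatment does not require open-label reading. In a single-centre trial, though, biopsies that travel the ordinary clinical route can reach the reader with the regimen known, and nothing in the text prevents it. Borderline rejection and the extent of fibrosis or tubular atrophy are matters of judgement, and no stated criterion limits that judgement here.

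The protocol also records what its authors expect. The Background reports their retrospective conclusion that conversion did not raise rejection risk, with a trend to better GFR. The Biopsy section treats fibrosis as typical of calcineurin inhibitors. A reader who knows the arm may know the expected answer.

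The result would be misclassification that differs by arm. It could create a difference or hide a real one. More subjects would not remove it.

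**Working it through.** **1. The plan's own biopsy count.** Randomization gives 275 subjects, allocated 2:1. Biopsy gives 70%, as 46 + 93 = 139.

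- 0.70 × 275 = 192.5, or about 64 and 128 by arm. This does not reproduce 139.
- 139 / 275 = 50.5%, and 139 / 0.70 = 198.6. The stated counts fit an enrolment of about 200: 0.70 × 200 = 140, or 46.7 and 93.3.

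The two sections need reconciling, as does the direction of the ratio: Randomization names tacrolimus first in its 2:1, while Biopsy implies two sirolimus subjects for each tacrolimus subject. I use the stated 46 and 93, and show 92 and 183 (275 split 1:2) for comparison. The point itself does not depend on either count.

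**2. Model for the size of the bias.** The documents give no rejection rate and no reader error, so both are assumed. Let the true rate p be equal in both arms, and let the reader call positive a share e of true negatives in the sirolimus arm only.

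- Tacrolimus: p1 = p. Sirolimus: p2 = p + e(1 − p). Shift: d = p2 − p1.
- Pooled rate: P = (n1·p1 + n2·p2)/(n1 + n2).
- s0 = √[P(1 − P)(1/n1 + 1/n2)]; s1 = √[p1(1 − p1)/n1 + p2(1 − p2)/n2].
- False-positive rate of the two-sided 5% test (the chi-square equivalent) = Φ[(d − 1.96·s0)/s1] + Φ[(−d − 1.96·s0)/s1].

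**3. Worked case: n1 = 46, n2 = 93, p = 0.10, e = 0.05.**

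- p2 = 0.10 + 0.05 × 0.90 = 0.145; d = 0.045; P = 0.1301.
- s0 = 0.0606, so 1.96·s0 = 0.1189; s1 = 0.0574.
- Φ(−1.288) + Φ(−2.857) = 0.0989 + 0.0021 = 10.1%.

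With e = 0.02: p2 = 0.118, and the result is 0.0460 + 0.0098 = 5.6%.

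In slides, there are 0.90 × 93 = 83.7 true negatives, so e of 2% to 5% means 1.7 to 4.2 over-called biopsies.

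**4. Range.**

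| True rate | e | Read rate, sirolimus | False positives, 46 vs 93 | False positives, 92 vs 183 |
|---|---|---|---|---|
| 5% | 2% | 6.9% | 6.0% | 8.2% |
| 5% | 5% | 9.75% | 13.4% | 25.2% |
| 10% | 2% | 11.8% | 5.6% | 6.7% |
| 10% | 5% | 14.5% | 10.1% | 16.8% |
| 30% | 2% | 31.4% | 5.2% | 5.5% |
| 30% | 5% | 33.5% | 6.7% | 8.7% |

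Expected events are few (0.10 × 46 = 4.6), so I checked the approximation. Summing the two binomial probabilities over all pairs of counts that the test rejects, for 46 vs 93 at p = 0.10, gives 5.3% at e = 2% and 10.2% at e = 5%.

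**5. Against sampling error.** The 95% half-width at 10% is 1.96·√[0.09(1/46 + 1/93)] = 10.6 points. The assumed shift is 1.8 to 4.5 points.

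No such figure can be given for fibrosis, because the plan states neither a scale nor a threshold.

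**The case against.** The strongest reply is that the protocol is silent on masking, and silence does not show unmasked reading. That stands: the finding is that masking is not specified, not that the reader knew the arm. The assumed bias is also smaller than the sampling error, and at 2% over-calling the inflation is slight. Allograft pathology is not among the aims listed under Research Objective. These points limit the weight of the finding but do not remove it.

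A reader might infer more than the documents support:

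- **That the pathologist is an investigator.** The monitoring plan says "All physicians associated with the Solid Organ Transplant Department are listed as either the PI or Sub-I's with this study". That concerns one department, and nothing places the pathologist in it.
- **That masking is free.** No reader, workflow or cost is described. Relabelling and a short delay are real, if small, costs.
- **That for-cause biopsies should be masked too.** Those readings lead directly to treatment. Withholding the regimen there touches clinical care and might need a separate research read.
- **That masking would secure the primary endpoint.** Clinicians know the arm when deciding whom to biopsy, and under Post randomization only the sirolimus arm has weekly labs during conversion. A masked reader would still report any imbalance this creates.

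**Conclusion.** The point holds for the scheduled biopsies. With open-label drugs and no masked reading specified, the 24- and 48-month pathology comparison, and any rejection found on those biopsies, can be biased by knowledge of the arm. The planned analyses cannot repair that.

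The size is illustrative only. It rests on an assumed 10% true rate, over-calling confined to the sirolimus arm, and the stated 46 and 93 biopsies. On those terms a nominal 5% error rate becomes about 6% to 10%. Lower true rates make it worse and higher ones milder. Under-calling, or over-calling in the other arm, would change the direction.

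This is a cheap improvement worth making. It does not show that results were biased, and it does not settle how rejection on for-cause biopsies was read.

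**What to change.** Add to the Biopsy section that the scheduled 24- and 48-month biopsies are labelled by study code and graded by the usual pathologist against stated criteria for rejection, fibrosis and tubular atrophy, with the regimen withheld until the grade is recorded. Name the criteria there, because masking without a stated scale does not make the reading reproducible.

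Leave for-cause biopsies on the normal clinical pathway. Have the report state that rejection on for-cause biopsies was read unmasked, and that masked reading does not remove bias in who is biopsied.

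The cost is a protocol addition, relabelling, and a short delay before clinical context reaches the pathologist. It needs no added reader, no added procedure and no change in sample size.
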